Heart Rate Response to Regadenoson and Sudden Cardiac Death

Study Protocol & Statistical Analysis Plan

NCT01842035

January 14, 2021

[name] Principal Investigator
University of Alabama at Birmingham
Birmingham, AL 35294

Heart rate response to regadenoson and sudden cardiac death

Objectives:

The main objectives of this proposal are to investigate whether:

1. A blunted heart rate response to regadenoson is an independent predictor of sudden cardiac death.
2. A blunted heart rate response to regadenoson can be used as a predictor of response to implanted cardiac defibrillator (ICD) on top of traditionally used indicators.

Hypotheses:

1. Patients with a blunted heart rate response to regadenoson are at higher risk of sudden cardiac death (death or appropriate cardiac defibrillation). This risk is maintained after controlling for age, gender, left ventricular ejection fraction, heart failure symptoms and medication use.
2. Patients with a normal heart rate response to regadenoson have a low rate of events (death or appropriate cardiac defibrillation) despite meeting current indications for having an ICD.

Background:

In patients with left ventricular systolic dysfunction and in those with a history of sudden cardiac death, an ICD reduces mortality.¹⁻³ However, not all patients with an ICD receive appropriate therapy from it (In a large study, only one third of patients received appropriate therapy from an ICD over the first 3 years of follow-up)⁴, and inappropriate ICD shocks are common and are associated with worse quality of life and increased mortality.⁵ Furthermore, ICDs are expensive (the procedure costs ~\$35,000) and place a toll on the health care system. Establishing a better predictor of risk of sudden cardiac death and of response to ICD is desirable.

Adenosine and regadenoson are routinely used as pharmacological stress agents to induce coronary hyperemia for myocardial perfusion imaging (MPI) in lieu of exercise. The increase in heart rate seen during adenosine infusion has previously been attributed to its vasodilatory effect on the systemic circulation and has thus generated little interest. Recently, it was recognized that this rise in heart rate is related to a direct stimulation of the sympathetic nervous system by adenosine therefore allowing for a novel simple method for the evaluation of autonomic function.⁶ Using data from the ADenoscan Versus RegAdenoson Comparative Evaluation for Myocardial Perfusion Imaging (ADVANCE MPI 1 and 2) Trials, we demonstrated that patients with diabetes mellitus have a blunted heart rate response to adenosine presumably due to cardiac autonomic dysfunction.⁷ Furthermore, the heart rate response associated with multiple risk factors of sudden cardiac death.^{7, 8} Since cardiac autonomic dysfunction has been linked to increased

cardiovascular risk,⁹ we postulated that the heart rate response may carry useful prognostic information. Recently we showed that a blunted heart rate response to adenosine is associated with increased mortality in the overall population and that it assisted in the risk stratification of patients at high risk (such as those with diabetes mellitus or chronic kidney disease) when added to traditional MPI findings.¹⁰ In a Cox regression model, a blunted heart rate response was the strongest predictor of mortality and provided additional prognostic data to MPI after controlling for age, gender, race, history of myocardial infarction, diabetes mellitus, chronic kidney disease and beta-blocker use. We also demonstrated that a decreasing heart rate response to regadenoson is associated with stepwise increase in mortality.¹¹ In a Cox proportional model for mortality that adjusted for age, gender, diabetes mellitus, renal disease and MPI findings, heart rate response to regadenoson in the lowest quartile was independently associated with 5-fold increase in mortality compared to the highest quartile. Patients with a normal heart rate response had a relatively low annualized total mortality despite the presence of risk factors.

We propose that patients with a blunted heart rate response to regadenoson have an altered autonomic nervous system (cardiac autonomic neuropathy) that places them at higher risk of sudden cardiac death. Using this novel and easily measured parameter, we will be able to select patients who are high risk and will benefit from an ICD and, at the same time, identify patients who are at low risk of experiencing sudden cardiac death despite satisfying current criteria for having an ICD (mainly a low left ventricular ejection fraction). In this proposal, we will be able to verify this using a highly selected population that is being continuously monitored for the occurrence of ventricular arrhythmias through their implanted devices.

Study Design: Prospective Observational

Population:

A total of 150 patients (18-80 years) with an indication for ICD implantation for primary prevention of sudden cardiac death as defined in the current American College of Cardiology/American Heart Association/Heart Rhythm Society Practice Guidelines.¹² Specifically we will recruit:

1. Patients with left ventricular ejection fraction (LVEF) less than 35% due to prior myocardial infarction who are at least 40 days post--myocardial infarction and are in NYHA functional Class II or III.
2. Patients with nonischemic dilated cardiomyopathy who have an LVEF less than or equal to 35% and who are in NYHA functional Class II or III.
3. Patients with LV dysfunction due to prior myocardial infarction who are at least 40 days post--myocardial infarction, have an LVEF less than 30%, and are in NYHA functional Class I.

Protocol

1. Prior to the implantation of a clinically indicated ICD, the heart rate response to regadenoson will be assessed. Regadenoson will be administered intravenously as a fixed intravenous bolus dose of 400 µg followed by a 5 mL saline flush. Medications (including beta-blockers) will be withheld on the morning of the test. The heart rate and blood pressure will be measured at baseline and every minute after regadenoson bolus for at least 5 minutes and until the heart rate and blood pressure are clearly returning towards baseline. The peak heart rate will be defined as the maximum achieved heart rate after regadenoson injection. The peak blood pressure will be defined as the blood pressure when the systolic component is at a minimum during the test. The heart rate and blood pressure response will be calculated for each patient as the maximum percent change from baseline.^{7, 8} A heart rate response in the lowest tertile will be defined as blunted. A heart rate response in the highest tertile will be defined as normal. Secondary analyses will be performed with the heart rate response as a continuous variable and using the following cut-offs, <20% (blunted), ≥40% (normal).^{10, 11}
2. An ICD will be placed for clinical indications using standard techniques.

Follow-up: 2-years from the time of ICD implantation.

Duration of study: 4 years

Endpoints:

1. Primary Endpoint: Sudden cardiac death
2. Secondary Endpoints
 - a. All-cause death
 - b. First appropriate ICD therapy
 - c. All-cause death or first appropriate ICD therapy
 - d. Inappropriate ICD therapy

Patients will be followed up at 6 months intervals with ICD interrogation. ICD therapy (shocks or anti-tachycardia pacing) will be determined as appropriate or inappropriate by an experienced clinical electrophysiologist ([name]) after review of the intra-cardiac electrograms. If patient fails to show up at their scheduled appointment, patients or their designated relatives will be contacted to verify their status. In case of death, relatives will verify circumstances of death.

SCD will be strictly defined as death within 1 hour of symptom onset, or an unobserved death in which the patient was seen and known to be doing well within 24 hours of death. Survivors of aborted SCD, resuscitated cardiac arrest, and those receiving appropriate ICD therapy will also be considered to have experienced SCD and will be included in the primary end point.^{13, 14}

Sample Size:

In a recent study from our group, patients with ICD implanted for primary prevention at our center experienced an event rate of death or first appropriate ICD therapy ~ 20% over first 2 years.¹⁵ In our recent study on the heart rate response to regadenoson, patients in the lowest heart response tertile experienced a 4-fold increased risk of death compared to those in the highest tertile.¹¹ We believe that is a conservative estimate of risk for this study since the heart rate response should be a better predictor of sudden cardiac death than overall mortality. A sample size of 126 patients will provide a 90% power to detect a 4-fold increase in risk of the primary outcome for patients in the lowest compared to the highest tertile of the heart rate response to regadenoson (40% vs. 10% over 2 years) at a preset P value of 0.05. We plan for a sample size of 150 to account for any dropouts and or loss of follow-up.

Statistical Plan:

All statistical analyses will be carried out using SPSS version 17 for Windows (SPSS Inc., Chicago, Illinois). We will collect data on patient demographics (age, gender, race, education), patient characteristics (height, weight), co-morbidities (history of myocardial infarction, diabetes mellitus, hypertension, dyslipidemia, atrial fibrillation, stroke), prior cardiovascular procedures (percutaneous coronary intervention or coronary artery bypass grafting), habits (tobacco use), symptoms (NYHA classification), medication intake (aspirin, beta-blocker, calcium channel blocker, angiotensin converting enzyme inhibitor (ACE-I), angiotensin receptor blocker (ARB), aldosterone antagonist, loop diuretic, statin, insulin), electrocardiographic characteristics (left bundle branch block, right bundle branch block, QRS, QT, PR) and laboratory results (serum creatinine, electrolytes, brain natriuretic peptide).

The population will be divided into 3 groups with 50 patients in each group based on tertiles of the heart rate response on regadenoson. Continuous variables will be presented as mean \pm SD and discrete variables as frequencies and percentages. The chi-square test or an analysis of variance (ANOVA) will be used for the comparison of categorical variables. Continuous variables will be compared using the unpaired student t test or the Mann-Whitney U test, as appropriate. In order to determine the predictors of the HRR to regadenoson, a linear regression model will be constructed with the HRR as the dependent variable and all the characteristics that are associated with the HRR ($p < 0.2$) as independent variables. An estimation of the effect of each of the variables on the HRR will be determined based on the coefficient of the variable in the regression equation. Follow-up time will be calculated from the time of evaluation to sudden cardiac death or to end of follow-up censored at 2 years from time of evaluation. Event-free survival curves will be constructed using the product-limit method (Kaplan-Meier) and differences among survival curves will be estimated by the log-rank test. Cox proportional hazard analysis will be used to estimate unadjusted and age, gender and LVEF adjusted (multivariate) risks for sudden cardiac death. We will introduce interaction terms to test for interaction between HRR and the different variables in the model. Estimated risks will be reported as hazard ratios (HR) with correspondent 95% confidence intervals (CI). All tests will be 2-tailed, and a p value of < 0.05 will be considered statistically significant.

Amendments

During the conduction of the trial, the following amendment were introduced:

1. The original protocol enrolled patients with a clinical indication for an implanted cardiac defibrillator (ICD) for primary prevention of sudden cardiac death. We amended the protocol to enroll patients who are undergoing an ICD implantation or a generator exchange for clinical indications.

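### Objective 2 asks what heart rate response adds to traditional indicators, but no measure of incremental prediction is planned and the adjusted model covers age, gender and LVEF only

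*Combined protocol and SAP*

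**What the plan says.** Objective 2 is one of two main objectives and concerns HRR as a "predictor of response to implanted cardiac defibrillator (ICD) on top of traditionally used indicators". Hypothesis 2 puts it in testable form: "Patients with a normal heart rate response to regadenoson have a low rate of events (death or appropriate cardiac defibrillation" even though they meet current ICD indications. The Background states the intended use: "Using this novel and easily measured parameter, we will be able to select patients who are high risk", and also to identify low-risk patients among those who qualify for a device.

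The Population section builds eligibility from LVEF, NYHA class and aetiology (prior infarction or non-ischaemic), for example "Patients with nonischemic dilated cardiomyopathy who have an LVEF less than or equal to 35% and who are in NYHA functional Class II or III".

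The Statistical Plan sets out the outcome analyses:
- Kaplan-Meier curves, compared by a log-rank test.
- "Cox proportional hazard analysis will be used to estimate unadjusted and age, gender and LVEF adjusted (multivariate) risks for sudden cardiac death".
- Interaction terms between HRR and the other model variables.
- Hazard ratios with 95% confidence intervals as the reported effect measure.

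Item 1 of the Protocol section adds secondary analyses with HRR as a continuous variable and with cut-offs of below 20% and at least 40%.

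No section compares a model with HRR to one without it, or plans a C-index, reclassification, calibration, sensitivity or specificity. The traditional indicators are never turned into a covariate list.

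**The concern.** A claim that a marker works on top of existing indicators needs two things: a stated set of indicators to add it to, and an estimate of what the addition achieves. The plan has part of the first and none of the second.

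Followed as written, the study could report a large, significant hazard ratio and conclude that HRR can be used alongside current ICD criteria. It would not have adjusted for two of the three indicators that make up those criteria, nor shown how much better patients are sorted. That conclusion bears on who is judged to benefit from a device.

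**Working it through.** **1. The plan's own figure.** Inputs from Sample Size: 40% versus 10% at 2 years, 90% power, P value of 0.05; the Statistical Plan makes tests two-sided. With pooled p = 0.25,

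n = [1.96·√(2·0.25·0.75) + 1.2816·√(0.40·0.60 + 0.10·0.90)]² / 0.30² = (1.200 + 0.736)² / 0.09 = 41.7, so 42 per third.

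Then 3 × 42 = 126, as stated (power 90.2%). This powers an unadjusted comparison of two thirds. The plan gives no figure for Objective 2.

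**2. Implied hazard ratio.** ln(1 − 0.40) / ln(1 − 0.10) = 4.85.

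**3. Covariates side by side.**

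| Variable | Eligibility | Hypothesis 1 | Adjusted Cox model |
|---|---|---|---|
| Age, gender | age range only | yes | yes |
| LVEF | yes | yes | yes |
| NYHA class / heart failure symptoms | yes | yes | no |
| Aetiology | yes | no | no |
| Medication use | no | yes | no |

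**4. Does a hazard ratio fix the gain?** This was illustrated by simulation. Assumptions that are not in the documents: a normally distributed base risk score, HRR thirds with a log-linear effect, and correlation of 0 or 0.5 between HRR and the base score. Overall 2-year risk was set at 20%, as in Sample Size. The adjusted hazard ratio, lowest versus highest third, was 4.85 throughout this table.

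| Correlation | AUC of base score | Gain in AUC |
|---|---|---|
| 0 | 0.62 | 0.103 |
| 0 | 0.72 | 0.062 |
| 0 | 0.80 | 0.039 |
| 0.5 | 0.69 | 0.059 |
| 0.5 | 0.78 | 0.036 |
| 0.5 | 0.84 | 0.025 |

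With a hazard ratio of 3 the gain was 0.014 to 0.059, and with 2 it was 0.006 to 0.027. So a ratio of 3 over a weak base model can add more than 4.85 over a strong one.

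**5. Absolute risk in the normal third.** Kaplan-Meier curves can supply this. At the planned 10%, 5 events in 50 patients has an exact 95% CI of 3.3% to 21.8%, which includes the overall rate of about 20% in Sample Size.

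**6. Information available.** Assume a middle-third risk of 10% to 20%. The lower value is what an overall 20% implies: 3 × 0.20 − 0.40 − 0.10 = 0.10. With 50 per third, events = 50 × (0.40 + 0.10 + 0.10) = 30, up to 50 × (0.40 + 0.20 + 0.10) = 35. A model with age, gender, LVEF, aetiology, HRR and one or two NYHA terms has 6 or 7 parameters: 30/7 = 4.3 to 35/6 = 5.8 events per parameter. Item 3 of the Amendments shortens follow-up and reduces the sample without stating a new number, so the count is probably lower.

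**The case against.** The strongest reply is that the plan already addresses Objective 2. Under the Population criteria every patient meets a current ICD indication, so different absolute risks by HRR within that group are already stratification on top of selection. Kaplan-Meier curves give those risks, which is what Hypothesis 2 asks about. The Background describes current criteria as mainly low LVEF, and LVEF is in the Cox model. The test of HRR in that model is asymptotically equivalent to a likelihood-ratio test against the same model without HRR.

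Much of this stands. A reader might infer that hazard ratios and log-rank p-values are the only outcome results and cannot show added prediction at all. The documents do not support that: Kaplan-Meier risks and interaction tests are planned, and the adjusted Cox test is a valid test of information beyond age, gender and LVEF.

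What the reply does not cover is NYHA class and aetiology, which vary among enrolled patients and may account for part of any difference by HRR, and the size of the gain. Hypothesis 2 also gives no threshold for a low event rate.

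A second fair objection is that 4 to 6 events per parameter is thin, and a C-index change estimated from so few events could be nearly uninformative. That is a reason to keep it supportive and not make it the sole basis of the conclusion.

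**Conclusion.** The concern holds in a limited form. No measure of incremental predictive performance is planned for Objective 2. The adjusted model tests association beyond age, gender and LVEF only, and a hazard ratio does not give the size of a gain: 4.85 is compatible with an AUC gain of about 0.03 to 0.10 under the simulation's assumptions. The planned analysis of association is unaffected. This is an inexpensive improvement to how one main objective is answered.

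One further inference should be avoided. The planned risks, with an assumed middle third of 10% to 20%, give HRR thirds alone an AUC of 0.69 to 0.71, and a single AUC of that order has a standard error of about 0.055 with 30 to 35 events in 150 patients. Those figures describe HRR by itself under the pre-amendment design. They are neither the gain over a base model nor the precision of that gain.

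**What to change.** Add to the Statistical Plan, for Objective 2:

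1. A base Cox model with age, gender, LVEF, NYHA class and ischaemic versus non-ischaemic aetiology, with NYHA class coded in as few terms as possible.
2. The same model plus continuous HRR, with the likelihood-ratio test of the added term as the test of added information.
3. As supportive results, the change in C-index with an optimism-corrected bootstrap 95% CI, and the absolute event risk with CI by HRR third.
4. A sentence limiting any claim that HRR can be used on top of current indicators to what these results show.
5. The endpoint to be used, since Hypothesis 2 refers to death or appropriate defibrillation while the Cox model is specified for sudden cardiac death.

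The cost is SAP wording and a short analysis. LVEF is already in the planned model, and NYHA class and history of myocardial infarction are on the data list, so no new patients or visits are needed. SPSS 17 may need supplementing for the bootstrap. The downside is precision: with about 30 to 35 events at best, and probably fewer after the amendments, the C-index interval will be wide and the Objective 2 conclusion may have to be softer.

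### The response is a percentage of resting heart rate, but no planned model for sudden cardiac death adjusts for resting heart rate

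*Combined protocol and SAP*

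**What the plan says.** Item 1 of the Protocol section sets the scale: "The heart rate and blood pressure response will be calculated for each patient as the maximum percent change from baseline". The primary classification follows from it: "A heart rate response in the lowest tertile will be defined as blunted". The secondary analyses treat the response as continuous or use fixed cut-offs of "<20% (blunted), ≥40% (normal"), still as percentages.

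The resting value is available for every test: "The heart rate and blood pressure will be measured at baseline and every minute after regadenoson bolus".

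The Statistical Plan estimates by Cox regression "unadjusted and age, gender and LVEF adjusted (multivariate) risks for sudden cardiac death". Hypothesis 1 has a longer list: "This risk is maintained after controlling for age, gender, left ventricular ejection fraction, heart failure symptoms and medication use". Neither list includes resting heart rate. The variables to be collected include "electrocardiographic characteristics (left bundle branch block, right bundle branch block, QRS, QT, PR"), but again not resting heart rate.

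**The concern.** Two patients whose hearts speed up by the same number of beats get different percentages if their resting rates differ, and the one who starts faster looks more blunted. If resting rate is itself related to risk, part of any association between a blunted response and sudden cardiac death comes from the denominator.

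This bears on both objectives. The first is that the response is an independent predictor. The second is that it adds to the indicators already in use. The Background attributes the risk to an altered autonomic response and proposes to use the test to select patients for an ICD. Resting rate costs nothing to obtain and needs no drug, so a reader will ask whether the test tells more than the pulse taken before it. No analysis in the plan answers that.

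**Working it through.** **1. The target effect, for scale.** The Sample Size section plans for 40% versus 10% over 2 years, 90% power and P = 0.05; the Statistical Plan makes tests two-sided. With mean proportion 0.25:

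n per tertile = [1.960·√(2·0.25·0.75) + 1.2816·√(0.40·0.60 + 0.10·0.90)]² / 0.30² = (1.200 + 0.736)² / 0.09 ≈ 41.7, so 42.

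42 × 3 = 126, the plan's figure. The sample size is not in dispute; it fixes 4-fold as the effect sought.

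**2. Effect of the denominator.** Response = 100 × (peak − resting) / resting.

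| Rise | Resting 60 | Resting 90 |
|---|---|---|
| 17 bpm | 17/60 = 28.3% | 17/90 = 18.9% |
| 24 bpm | 24/60 = 40.0% | 24/90 = 26.7% |

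On the secondary cut-offs, 17 bpm moves from the middle group to blunted, and 24 bpm from normal to the middle group. A 15 bpm rise equals 20% at a resting rate of 15/0.20 = 75 bpm and is classed as blunted above that.

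**3. Whether any planned analysis removes it.**
- The regression that selects variables at p < 0.2 has the response as its outcome, so it does not adjust the sudden-death model.
- The interaction terms involve variables already in the Cox model.
- The continuous and fixed cut-off analyses keep the percent scale.
- No analysis uses absolute change in bpm.

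**4. Possible size.** The documents give no heart-rate distributions, so every input here is an assumption. I simulated 1,000,000 patients per scenario with the response having no effect on risk. Relative risk was h^((resting − mean)/10), with h = 1.1, 1.2 or 1.4 per 10 bpm. The ratio is mean risk in the lowest tertile of percent response over that in the highest.

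Rise independent of resting rate:

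| Resting mean/SD; rise mean/SD (bpm) | Correlation of resting rate with percent response | Mean resting rate, lowest vs highest tertile | Ratio at h = 1.1 / 1.2 / 1.4 |
|---|---|---|---|
| 72/12; 20/9 | −0.35 | 75.7 vs 66.8 | 1.09 / 1.18 / 1.36 |
| 75/13; 18/8 | −0.37 | 79.2 vs 69.1 | 1.10 / 1.21 / 1.42 |
| 70/10; 22/10 | −0.31 | 72.7 vs 66.2 | 1.06 / 1.13 / 1.25 |

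Across the three scenarios:
- rise half-proportional to resting rate: 1.03–1.05 / 1.06–1.10 / 1.12–1.20;
- rise fully proportional: 1.00 throughout.

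Even in the independent case, 43–46% of patients in the top third of resting rate are classed as blunted, against 33% if resting rate played no part.

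**5. Against the target.** The ratio is close to h^(difference in mean resting rate / 10); for the second scenario, 1.4^1.01 ≈ 1.40. A 4-fold ratio at that difference would need h ≈ 4^(1/1.01) ≈ 3.9 per 10 bpm. A wider setting (resting SD 14 bpm, h = 1.5) still gave only about 1.7.

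**6. Chance of a false positive.** With 50 per tertile and a 20% average event rate, a spurious ratio of 1.06 to 1.21 gives p < 0.05 in about 5–8% of trials, and 1.42 in about 14%.

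**7. Cost in the model.** Two tertile terms plus age, gender and LVEF make 5 parameters. At about 20% of 150 = 30 events, that is 30/5 = 6 events per parameter; a sixth parameter makes it 30/6 = 5.

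**The case against.** Percent change is a deliberate choice, cited to the group's prior work, and the expected 4-fold effect comes from that work. If the rise scales with resting rate, percent change is the right scale and the artefact is nil; nothing in the documents says otherwise. In the scenarios above, percent response correlates 0.91 to 0.94 with the absolute rise, so the predictor is mostly the response itself. Resting rate may also express the autonomic trait under study, so conditioning on it could remove real signal. The model is already thin, and the heart failure symptoms and medication use named in Hypothesis 1 are still missing from it.

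Most of this stands, and it limits both the size of the concern and the form of the remedy. A reader might infer that a fast resting rate alone puts a patient in the blunted tertile; the 43–46% figure shows that it shifts the odds and no more. The <20% cut-off in the worked example belongs to the secondary analyses; the primary definition is a relative tertile.

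The objection does not supply the missing analysis. Whether the rise is proportional to resting rate is unknown here, and the trial's own data can show it. Possible overlap with autonomic function is a reason to report the model both ways.

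**Conclusion.** The gap is real and moderate. As written, the plan cannot show that the response predicts sudden cardiac death independently of its own denominator. That rests on the document text alone.

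The size rests on assumptions: a spurious tertile ratio between 1.00 and 1.42, depending mainly on how far the rise scales with resting rate and on the risk per 10 bpm. A modest hazard ratio would be ambiguous. A reader might go further and infer that a positive result could be resting heart rate in disguise. The documents do not support that for a result near the planned 40% versus 10%, which this mechanism could not produce under any of the assumed settings.

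**What to change.** In the Statistical Plan:

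1. Prespecify an additional Cox model with age, gender, LVEF and baseline (pre-regadenoson) heart rate as one continuous covariate. Report it beside the planned model, not in its place.
2. Add baseline heart rate to the comparison of characteristics across tertiles.
3. Add a sensitivity analysis with absolute change in bpm as the predictor and baseline heart rate as a covariate.
4. State that any claim that the response predicts independently of, or adds to, resting heart rate rests on the model that includes it.

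No new data, patients or procedures are needed, because the baseline value is already recorded at each test. The cost is one parameter, taking about 6 events per parameter to about 5, and fewer if the shorter follow-up and smaller sample in item 3 of the Amendments reduce the events. Adjustment may also take out some true autonomic signal, which is why both models should be shown.

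### The event is defined in three ways that do not match (Hypotheses, primary endpoint, sample-size source), and pacing-only therapy is reported as sudden cardiac death

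*Combined protocol and SAP*

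**What the plan says.** Three sections of the combined protocol and SAP describe the event.

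- **Hypotheses.** Item 1 says that patients with a blunted response are at "higher risk of sudden cardiac death (death or appropriate cardiac defibrillation"). Item 2 says that patients with a normal response "have a low rate of events (death or appropriate cardiac defibrillation"). Neither restricts deaths by timing or cause, and the device component is defibrillation.
- **Endpoints.** The listed item is "Primary Endpoint: Sudden cardiac death". Its fatal part reads "SCD will be strictly defined as death within 1 hour of symptom onset, or an unobserved death in which the patient was seen" in good condition during the preceding 24 hours. Its non-fatal part adds aborted SCD, resuscitated arrest, and "those receiving appropriate ICD therapy will also be considered to have experienced SCD and will be included in the primary end point". Therapy is given as "ICD therapy (shocks or anti-tachycardia pacing"), which an electrophysiologist judges appropriate or inappropriate from the electrograms. For deaths, the section says only that relatives confirm the circumstances.
- **Sample Size.** The planning rate of about 20% over two years is for death or first appropriate ICD therapy. It introduces a power statement for the primary outcome: 126 patients, 90% power, 40% versus 10% in the lowest and highest tertiles.

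The Statistical Plan then runs follow-up time and the Cox models to sudden cardiac death, with no component breakdown.

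**The concern.** The objectives are to show that the heart rate response predicts sudden cardiac death and to find patients at low risk although they qualify for an ICD. Both claims depend on what is counted. Appropriate pacing is a treated arrhythmia, but it is neither defibrillation nor death. If pacing-only patients make up much of the event count, a positive result would carry the label sudden cardiac death while mainly describing pacing-terminated episodes. The fatal part raises a smaller problem of the same kind. It depends on timing and witnessing alone, so a plainly non-cardiac sudden death meets it as written. In the other direction, a patient who dies non-suddenly without earlier therapy is an event under the hypotheses and a non-event in the primary analysis. The plan contains nothing that would let a reader separate these contributions afterwards.

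**Working it through.** **Step 1. The definitions side by side.**

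| Component | Hypotheses | Primary endpoint | Planning rate (secondary endpoint c) |
|---|---|---|---|
| Sudden or unobserved cardiac death | counted | counted | counted |
| Sudden or unobserved death, evident non-cardiac cause | counted | counted as written | counted |
| Non-sudden death | counted | not counted | counted |
| Aborted SCD or resuscitated arrest without ICD therapy | not named | counted | not counted |
| Appropriate shock | counted | counted | counted |
| Appropriate pacing only | not counted | counted | counted* |

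*This assumes that the study behind the planning rate defined therapy as Endpoints does. The documents do not say.

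No two columns agree. The hypotheses and the primary endpoint differ in three rows: non-sudden death, arrest without therapy, and pacing only. The primary endpoint and the planning rate differ in two: non-sudden death, and arrest without therapy. Secondary endpoints b and c use the same definition of therapy, so neither isolates shocks.

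**Step 2. The plan's own figure.** Inputs from Sample Size and Statistical Plan: p1 = 0.40, p2 = 0.10, two-sided alpha 0.05, power 90%, three equal tertiles. With pooled variance and no continuity correction, and p̄ = (p1 + p2)/2 = 0.25:

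n = [1.960 × √(2p̄(1 − p̄)) + 1.282 × √(p1(1 − p1) + p2(1 − p2))]² / (p1 − p2)²

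= [1.960 × √0.375 + 1.282 × √0.33]² / 0.09 = 41.7, so 42 per tertile, and 3 × 42 = 126.

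Power at 42 per tertile is Φ[(0.30 × √42 − 1.960 × √0.375)/√0.33] = Φ(1.295) = 90.2%. The stated figure reproduces.

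**Step 3. Sensitivity range without pacing-only events.** The pacing-only share f is not in the documents. Assume that it is the share of patients with a primary event whose only event is pacing, and that it is the same in both tertiles. Then p1 = 0.40(1 − f), p2 = 0.10(1 − f), and the ratio stays at 4.

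| f | p1 vs p2 | Power, 42 per tertile | Power, 50 per tertile | Total N for 90% |
|---|---|---|---|---|
| 0% | 40% vs 10% | 90.2% | 94.6% | 126 |
| 10% | 36% vs 9% | 85.5% | 91.1% | 147 |
| 20% | 32% vs 8% | 79.6% | 86.2% | 171 |
| 30% | 28% vs 7% | 72.4% | 79.8% | 201 |
| 40% | 24% vs 6% | 64.1% | 71.9% | 243 |
| 50% | 20% vs 5% | 54.8% | 62.4% | 303 |

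Example at f = 50%, with p̄ = 0.125: Φ[(0.15 × √42 − 1.960 × √0.21875)/√0.2075] = Φ(0.122) = 54.8%.

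These figures describe a supplementary analysis. They do not give the power for the event in the hypotheses, because that event also includes non-sudden deaths, which would have to be added back. The documents do not give their number, so the net change could go either way. The figures also use the sizes in Sample Size. The Amendments section records a reduction in sample size and follow-up without giving a new number.

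**The case against.** Counting appropriate therapy as equivalent to sudden cardiac death is explicit, written in advance and supported by citations. Only therapy judged appropriate on the electrograms counts. Hypothesis 1 names sudden cardiac death as its outcome, the event sets overlap heavily, and secondary endpoints a to c report death, appropriate therapy and their combination. All of this stands. It defends the broad composite as a legitimate choice of primary endpoint. It does not answer the mismatch between sections, nor the lack of any analysis that separates pacing from shocks, because an appropriate pacing episode still counts in the primary endpoint and in secondary endpoints b and c.

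A reader might infer two stronger points, and the documents support neither.

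- *That the death rule departs from the hypotheses because it ignores cause.* The hypotheses count any death, so a non-cardiac sudden death lies inside the hypothesised event. The missing cause condition conflicts only with the label sudden cardiac death. On deaths, the departure from the hypotheses is the omission of non-sudden ones.
- *That the study is underpowered.* The 90% is stated for the primary outcome and reproduces. The lower figures rest on assumed shares and belong to an analysis that the plan does not make. At a 10% share and 50 per tertile, even that analysis keeps 91.1%.

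**Conclusion.** The point holds as a problem of definition and reporting. The hypotheses, the primary endpoint and the planning rate use three different events. As written, pacing-only therapy and plainly non-cardiac sudden deaths are analysed as sudden cardiac death, and non-sudden deaths drop out of the primary endpoint although the hypotheses include them. This follows from the text and needs no assumption, apart from how the source of the planning rate defined therapy.

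It would go too far to say that the primary analysis does not test the hypothesis. It tests an overlapping event set under a label narrower than its content. How much this matters depends on the pacing-only share and the number of non-sudden deaths, and the documents give neither. The range of about 85% to 55% for shares of 10% to 50% (42 per tertile, 4-fold ratio kept) shows only how far a restricted analysis might lose precision. The change is worth making because it is cheap and determines whether the result can support a claim about sudden cardiac death.

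**What to change.** 1. Use one event definition in Hypotheses, Endpoints and Sample Size. State whether pacing-only therapy and non-sudden deaths count.
2. In Sample Size, state that the planning rate of about 20% belongs to secondary endpoint c, and say why it is taken to apply to the primary endpoint.
3. If the broad endpoint stays primary, reword both hypotheses to match it and describe it as *sudden death or appropriate ICD therapy*, naming aborted SCD and resuscitated arrest in the definition.
4. Pre-specify a sensitivity analysis limited to sudden death without evident non-cardiac cause, aborted SCD or resuscitated arrest, or appropriate shock. A patient whose first event is pacing remains at risk and counts at a later qualifying event.
5. Report component counts (death, shock, pacing only) by tertile.

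The device part needs no new data, because the electrograms are already reviewed. The death part needs a short rule for judging evident non-cardiac cause from the circumstances that relatives report. The downside is that the sensitivity analysis has fewer events and wider intervals, so it should be presented as supportive, without a power claim.
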